Official title: Non-invasive Transcranial Direct Current Stimulation to Improve Cognitive Efficiency

NCT number: NCT05216315

Document date: July 28, 2023

Study Protocol

Eligibility Criteria:

Participants eligible for inclusion in the study must meet specific criteria based on their age, cognitive status, and health condition. For healthy older adults, the minimum age requirement is 65 years, and they must have a Montreal Cognitive Assessment (MCA) score greater than 26 points and a Geriatric Depression Scale (GDS) score between 1 and 3. Individuals classified as having Mild Cognitive Impairment (MCI) must also be at least 65 years old and have a MCA score between 21 and 26 points, with a GDS score falling between 1 and 3. Those categorized as having mild Alzheimer's disease (EA) must meet the same minimum age requirement of 65 years, with a MCA score ranging from 18 to 23 points and a GDS score between 3 and 4.

Exclusion Criteria:

Certain conditions disqualify individuals from participating in the study. These include contraindications to transcranial Direct Current Stimulation (tDCS), such as the presence of intracranial metal implants, intracranial hypertension, or a high risk of seizures. Additionally, significant asymptomatic neurovascular disease, a history of previous symptomatic stroke, alcohol or drug abuse/dependence, severe psychiatric symptoms, or depressive symptoms higher than mild are grounds for exclusion from the study.

Randomisation

Once patients were available, allocation to the anodal and sham tDCS groups was carried out by stratified block randomisation. Participants were randomly assigned using a random number system. They were randomly assigned to the experimental groups (anodal vs. sham) with a 1:1 ratio, with gender as the stratum. Participants did not know which group they had been placed in until the intervention ended, this being a single-blind study.

Procedure

Stimulation was performed using an HDC stimulator (Newronika TM, Milan, Italy), which is battery-driven and delivers a direct current. The current intensity was 2 mA, and the stimulation lasted 20 minutes. In addition, a current ramp was delivered for 30 seconds prior to the start and end of stimulation. A pair of 25 cm² rubber electrodes

transferred the direct current. These electrodes were inserted into sponge pads soaked with sterile water. The electrodes and sponges were placed in a neoprene headcap with predefined and clearly annotated positions, based on a subset of the international 10-10 EEG system. The anode was placed on F3 at left dorsolateral prefrontal cortex (DLPFC), and the cathode was placed on the right frontal lobe (Fp2). Electrode placement and session duration were identical in active and placebo tDCS. However, in the placebo tDCS condition, at the end of the onset ramp, the current was automatically turned off for 20 minutes and then turned on again for the last 30 seconds.

In addition, to check the stimulations carried out, the HDCstim® stimulator is connected to the HDCprog, which has a “treatment report” in its menu. These reports show: a. Time and date of each stimulation, b. Average impedance of each stimulation (a suitable impedance range would be from 4 kOhm to 12 kOhm, and c. Result of the treatment (completed, failed or cancelled).

Additionally

Participants were fully informed about the study's blinding design and provided informed consent acknowledging their understanding and acceptance of the blinding procedure. Quality control measures were implemented to maintain consistency and accuracy in tDCS administration. Personnel received training in standardized electrode placement procedures and stimulation administration. Ongoing supervision ensured proper electrode placement and adherence to established protocols in all stimulation sessions, ensuring uniform treatment administration throughout the study.

Outcome

The primary outcome measures were general cognitive function, immediate and delayed memory, and learning ability. The secondary outcome measures included executive function tests. The selection of primary outcomes was based on the DSM-5 criterion (APA, 2013) that states that mild neurocognitive disorder due to possible Alzheimer's disease should show clear evidence of a decline in memory and learning. The assessment of memory and learning is a main criterion in the characterisation of the pathology, and we aimed to analyse the possible change in measures that analyse these variables. In addition, given that the progression of these patients to major neurocognitive disorder due to Alzheimer's disease is usually accompanied by a deterioration in executive control, change in the measures that assess this variable was proposed as a secondary outcome.

The Mini-Mental State Examination (MMSE; Folstein et al., 1975) was used as an index of global cognitive functioning; the maximum score is 30 points. This test was designed to estimate the existence and severity of cognitive impairment; it is a brief and quantitative test that measures general cognitive function.

Test de Aprendizaje Verbal Complutense (TAVEC; Benedet and Alejandre, 1998). This test presents a list of 16 words which, after being read by the evaluator, have to be repeated by the participant. The list is repeated five times (trials), and after 20 minutes, the participant is again asked to remember the 16 words. The test was administered to evaluate the participant's immediate memory (Trial 1), learning ability (analysing Trial 5 and the total number of correct answers on the five trials), and delayed memory.

Memory Alteration Test (M@T; Rami et al., 2007). The M@T provides efficient and valid screening for A-MCI and early-stage AD. The test evaluates different abilities such as: encoding, orientation, semantic memory, and free recall. The maximum score is 50 points.

Direct and inverse digits of the Wechsler Intelligence Scale for Adults-III (Wechsler, 2001). These tests assess attentional capacity by exposing the participant to increasing amounts of information. On the direct digits task, which is used to assess immediate recall, the subject must repeat the sequence of numbers in the same order in which they are read by the examiner. On the inverse digits task, which assesses working memory and mental flexibility, the subject must say the digits backwards from the way they were presented by the examiner. Both tests are evaluated in the same way, assigning one point for each correct item, with a maximum score of 16 for both tests.

Rey's Complex Figure (Rey, 1984). This test is used to evaluate both memory and executive capacity, such as planning, motor skills, working memory, and visuoconstructive and spatial ability. For its execution, the subject has to attentively reproduce a complex geometric drawing and later reproduce it after a three-minute delay.

Semantic fluency and phonological fluency subtests of the Barcelona Test Revised (TBR; Peña-Casanova 2005). The semantic fluency subtest requires the subject to evoke the maximum number of words linked to a specific category, "animals", in one minute. In the case of phonological verbal fluency, the subject is asked to recall the maximum number of words beginning with the letter "p" in a maximum of 3 minutes. This test evaluates the ability to access and recall elements from the lexical and semantic store. Among the processes involved, information processing speed, cognitive flexibility, and

working memory have been pointed out.

Statistical Analysis

A priori power calculation for ANOVA repeated-measures within-between interaction required a total sample of 32 participants to detect an effect size of .30 with 90% power, with alpha set at .05. Power calculations were carried out using GPower 3.1.7.

To analyse the sociodemographic variables, we used independent samples t-tests and chi-square tests. To analyse the cognitive variables, mixed ANOVAs with 2 groups (active vs. sham; between-subjects) X 2 sessions (before vs. after intervention; within-subjects) were conducted. The effectiveness of the tDCS should be reflected by finding a significant interaction between the two independent variables (in which the active group should improve across sessions, whereas the sham or control group would not). Post-hoc simple effects tests were conducted to analyse these significant interactions. A value of $p \leq .05$ was considered statistically significant. Data were analysed using SPSS 28.

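### Randomisation is stratified by gender but the efficacy ANOVA omits it, so the group x session test is conservative for any outcome where gender predicts change

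*Combined protocol and SAP*

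**What the plan says.** The Randomisation section of the combined protocol and SAP says that allocation "was carried out by stratified block randomisation", "with a 1:1 ratio, with gender as the stratum". Gender is the only stratum named, and no block size is given.

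The Statistical Analysis section says that for the cognitive variables "mixed ANOVAs with 2 groups (active vs. sham; between-subjects) X 2 sessions (before vs. after intervention; within-subjects) were conducted". Effectiveness "should be reflected by finding a significant interaction between the two independent variables", so the group x session term carries the efficacy claim for every primary and secondary outcome. Gender does not appear in any efficacy model. The only other tests listed are t-tests and chi-square tests on sociodemographic variables.

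The same section states that the power calculation "required a total sample of 32 participants" "to detect an effect size of .30 with 90% power", "with alpha set at .05".

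**The concern.** In a two-arm, two-session mixed ANOVA, the group x session test is the same as a two-sample t-test on the before-after change. Stratified blocks balance gender across arms, so any gender difference in change drops out of the real sampling variability of the arm contrast. The planned model has no term to take that difference out of the error, so it stays in the residual. The test then compares an arm difference that is stable with respect to gender against a residual that is not.

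Only a gender difference in change matters. A gender difference in level cancels when the sessions are subtracted, so the missing term is gender x session. What is at stake is efficiency: a test that runs below its nominal level, and a real effect that is somewhat harder to detect than it would be if the analysis followed the randomisation.

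**Working it through.** **Inputs from the documents.** Total N = 32, 1:1 (16 per arm); effect size .30, read as Cohen's f because a G*Power repeated-measures ANOVA is named; power 90%; alpha .05; two groups, two sessions.

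**Inputs assumed.** The documents do not state the pre-post correlation or the sphericity correction; 0.5 and 1 are used. They also do not give the share of variance in change that gender explains (R2); 0 to .20 is shown.

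**Step 1: reproduce the stated sample size.** For the within-between interaction with m = 2 sessions:

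λ = f² × N × m / (1 − ρ) = .09 × 32 × 2 / 0.5 = 11.52, with 1 and 30 df.

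Power is 0.907, against 0.887 at N = 30, so N = 32 reproduces. It depends on ρ: at ρ = 0.3 the required N is 44, and at ρ = 0.7 it is 20.

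**Step 2: express the design effect as a change-score difference.** For a two-sample t-test with 16 per arm, λ = N × d² / 4 = 8d². Setting 8d² = 11.52 gives d = 1.2 SD of change.

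**Step 3: size of the error-term mismatch.** Scale change to unit within-arm variance, with gender explaining R2 of it and balanced exactly across arms.

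- True variance of the arm difference: (1 − R2) × (1/16 + 1/16) = (1 − R2)/8.
- Expected variance reported by the planned model (30 error df): [(1 − R2) + (32/30) × R2]/8.
- Ratio of standard errors: √{1 + (32/30) × R2/(1 − R2)}.

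At R2 = .05 the ratio is √1.056 = 1.028; at .10, √1.119 = 1.058; at .20, √1.267 = 1.125. The reported standard error is therefore about 3%, 6% and 13% too wide.

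**Step 4: effect on the test.** The adjusted test has 1 and 29 df with λ = 8d²/(1 − R2). The planned test was evaluated by simulation with gender balanced across arms and checked by numerical integration.

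| R2 (assumed) | Type I, planned | Power d = 1.2, planned / adjusted | Power d = 0.8, planned / adjusted |
|---|---|---|---|
| 0 | 5.0% | 90.7 / 90.7% | 59 / 59% |
| .01 | 4.9% | 90.8 / 90.9% | 59 / 59% |
| .05 | 4.4% | 91.2 / 92.0% | 59 / 61% |
| .10 | 3.9% | 91.7 / 93.3% | 59 / 64% |
| .20 | 2.8% | 92.7 / 95.6% | 59 / 69% |

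Type I error with gender in the model is about 5.0% throughout. The d = 0.8 column is a smaller effect chosen for illustration; it is not in the documents.

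**Step 5: robustness to imperfect balance.** A 20/12 gender split gives the same results. With permuted blocks of 4 (an assumed size) and a 21/11 split that leaves blocks incomplete, planned type I error is 4.5%, 3.9% and 3.0% at R2 = .05, .10 and .20.

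**The case against.** The premise is not in the documents: no section reports a gender effect on change for any outcome, and no reason is given to expect one of 10 or 20%. The error is also in the safe direction, and several outcomes are each tested at .05 with no stated multiplicity adjustment, so a slightly conservative individual test is a minor fault. The larger gains need an effect below the one the trial was powered for. All of this stands. It limits the size of the point but does not remove the mismatch between randomisation and analysis, or the fact that correcting it costs almost nothing.

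Three stronger readings might be inferred, and the documents support none of them.

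- That every primary and secondary p-value is conservative. This would need gender to predict change on every outcome, and nothing shows that.
- That the trial falls short of its stated power. In the table, planned power at d = 1.2 rises slightly with R2 and does not fall below 90%. The loss is only relative to the adjusted test.
- That the benefit of stratifying is thrown away. With gender exactly balanced, the adjusted and unadjusted estimates of the arm difference coincide, so the estimate already has the smaller sampling variability. Only the reported standard error and the test are affected.

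The Statistical Analysis section is also written in the past tense. If analysis is complete, replacing the primary model would be a post hoc change.

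**Conclusion.** The point holds conditionally. The omission of the stratum and the direction of its effect are certain from the text; the size is not. For an outcome where gender predicts change, the planned test is conservative and less powerful than the gender-adjusted one. At the design effect the difference is modest, and it becomes material only if the true effect is smaller and gender explains a substantial share of change. These figures rest on an assumed R2, on near-balance of gender across arms and, for the translation of f = .30 into d = 1.2, on a correlation of 0.5. This is a sound efficiency improvement that should be made. It is not a threat to the validity of a positive result.

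**What to change.** In the Statistical Analysis section, add gender as a between-subjects factor, together with its gender x session term, to each efficacy model, and take the group x session test from that model. A gender main effect without the session term would not help, and no gender x group x session term is needed for this test.

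The cost is one sentence and one error degree of freedom (29 instead of 30). If gender explains nothing, power at the design effect goes from 0.9072 to 0.9065. Gender had to be known to randomise, so no new data are needed.

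If outcome data have already been analysed, keep the planned ANOVA, report the gender-adjusted result beside it, and state that the adjustment was added later.

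### Four unranked primary domains, carried by at least five scores, are each tested at .05 with no correction, order or success rule, so the false-positive rate is uncontrolled

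*Combined protocol and SAP*

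**What the plan says.** The Outcome section lists the primaries in one sentence, with none placed first: "The primary outcome measures were general cognitive function, immediate and delayed memory, and learning ability". It explains the choice by a diagnostic criterion and adds that "we aimed to analyse the possible change in measures that analyse these variables". On the other tier it says only: "The secondary outcome measures included executive function tests".

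The test descriptions then link scores to domains. Of the MMSE, the plan says "it is a brief and quantitative test that measures general cognitive function". The TAVEC is given for "immediate memory (Trial 1), learning ability (analysing Trial 5 and the total number of correct answers on the five trials), and delayed memory". That makes five scores for four domains, with two of them serving learning.

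Three further measures are described in memory terms but given no tier:
- M@T: "The test evaluates different abilities such as: encoding, orientation, semantic memory, and free recall".
- Digit span forwards: "On the direct digits task, which is used to assess immediate recall".
- Rey's figure: "This test is used to evaluate both memory and executive capacity", with a delayed redrawing.

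The Statistical Analysis section applies 2 × 2 mixed ANOVAs to the cognitive variables. It looks for efficacy in the group-by-session interaction, describes the expected pattern (active improves, sham does not), follows significant interactions with post hoc simple effects, and uses one threshold of .05. The sample size of 32 is for one interaction test: effect size .30, 90% power, alpha .05.

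**The concern.** The plan does not define a positive trial. It does not say how many primaries must succeed, in what order they are tested, how alpha is shared, or whether the simple-effects pattern is a formal condition. It also leaves open whether the primary family has five scores or as many as eight. With several chances to win at .05 each, a favourable result on any one of them can be reported as a primary success, and the choice of which scores count as primary can follow the results. The error rate of the main efficacy claim is then neither stated nor held at 5%. The quoted power does not describe any decision taken across the family.

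**Working it through.** **Inputs from the documents.** N = 32, 1:1 allocation (so 16 per arm), effect size f = .30, alpha .05, two sessions, five scores explicitly tied to primary domains. **Assumed, because the plan is silent:** pre-post correlation r, correlation between the change scores, and success declared on one significant primary interaction.

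**1. The plan's own sample size.** For the within-between interaction, λ = f² × N × m / (1 − r), with m = 2 and df 1 and 30. At r = .5, λ = .09 × 32 × 2 / .5 = 11.52, and power is 90.7%. The stated 32 is therefore reproduced, for one test at .05. At r = .3 the required N would be 44, and at r = .7 it would be 20.

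**2. False positives with no true effect.** The 2 × 2 interaction F test is equivalent to a two-sided t test on change with 30 df. For five independent scores:
- at least one false interaction: 1 − .95⁵ = 22.6%;
- at least one favouring active: 1 − .975⁵ = 11.9%.

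For correlated scores, null trials were simulated (16 per arm, equally correlated normal changes, 400,000 trials per setting):

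| Between-score correlation | 0 | .5 | .7 | .9 |
|---|---|---|---|---|
| Five scores, any false interaction | 22.6% | 18.5% | 15.0% | 10.4% |
| Five scores, favouring active | 11.9% | 9.3% | 7.5% | 5.1% |
| Eight scores, any false interaction | 33.6% | 25.3% | 19.5% | 12.2% |
| Eight scores, favouring active | 18.3% | 12.7% | 9.7% | 6.1% |

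The comparators for one test are 5% and 2.5%. For five scores, the rate favouring active is thus 5.1/2.5 ≈ 2.0 to 11.9/2.5 ≈ 4.8 times that of a single test.

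**3. Part-whole overlap.** Trials 1 and 5 are components of the five-trial total, so zero correlation is an upper bound. With the total built as the sum of its trials, and assumed correlations of .2–.7 among TAVEC changes and 0–.5 between MMSE and TAVEC, the rates are 15–21% for any false interaction and 7.6–10.7% favouring active.

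**4. If the full pattern is required.** Suppose success also needs a significant gain in active and none in sham. Five scores then give 1.9–4.0% with no practice gain, against 0.8% for one score. With a shared gain of .25–.75 SD of change they give 4.1–11.3%, against 1.7–2.4%.

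**5. Holm.** For five scores the smallest p-value is compared with .05/5 = .01, the next with .05/4 = .0125, and so on. The simulated familywise error is 2.4–4.9% for five scores and 1.9–4.9% for eight. If Holm covers only five scores while the other three are also treated as primary and read at .05, the error is 8.6–18.4%.

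**6. Power under Holm.** At r = .5, λ = 11.52 corresponds to a between-arm difference of 1.2 SD of change (8 × 1.2² = 11.52). One named score at alpha .01 has 73.5% power. The power for at least one Holm win among five, over between-score correlations of 0 to .9, is:

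| Pre-post r | One score affected | Two affected | All five affected |
|---|---|---|---|
| .3 | 55–57% | 63–80% | 70–98% |
| .5 | about 74% | 80–93% | 85–99.9% |
| .7 | 94% | 96–99.7% | 98–100% |

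Among eight scores at r = .5, it is 67–68% with one affected, 74–89% with two, and 83–100% with all eight.

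**The case against.** The strongest reply is that the plan does not treat any p-value at or below .05 as success. It describes a direction and a pattern, and an interaction favouring sham would not count. That is fair: the 5–12% range favouring active is closer to the plan's intent than 10–23%, and if the full pattern were binding with no practice gain, the rate would be below 5%. But the plan presents simple effects as follow-up tests and not as a condition. Even under that reading, several scores still carry more than twice the false-benefit rate of one.

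A second reply is that the ends of the correlation range are unlikely. This also has force, and the part-whole model narrows the range to 7.6–10.7% favouring active, still at least three times 2.5%.

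Third, the family could be smaller or larger. With one score per domain (four scores), the rates are 9.5–18.5% for any false interaction. The digit tasks are introduced as attention measures and the M@T as a screening tool, so eight is best kept as a sensitivity case.

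Fourth, Holm with one win is only one valid choice. A single primary, a fixed order, or a requirement that all primaries succeed would also control error. That stands where the data are unseen. Once results are known, a primary or an order picked afterwards gives no protection, whereas Holm needs no ranking, although it still depends on the family.

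**Conclusion.** The concern holds. The absence of a correction, an order and a success rule is plain from the text, and the stated power covers one uncorrected test only. How large the inflation is depends on assumptions the documents cannot settle: a one-win rule, 16 per arm, and the correlation between change scores. With five scores and a one-win rule, the false-benefit rate exceeds that of a single test by a factor of about two to nearly five across all the correlations examined. This should be fixed before any efficacy claim rests on these outcomes.

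**What to change.** 1. Fix the primary family from records made before the data were seen, and settle the tier of the M@T, digit span forwards and Rey recall. If no such record exists, use the five scores explicitly tied to the primary domains, state that this was a later choice, and show Holm across all eight memory-related scores as a sensitivity analysis.
2. Apply Holm to every interaction p-value in the family at familywise .05.
3. Define success as at least one Holm-significant interaction favouring active, and say whether the simple-effects pattern is also required.
4. Treat all other scores as secondary or exploratory, with no efficacy claim.
5. Restate power with its assumptions. Label 73.5% as the power for one named score at alpha .01 (f = .30, N = 32, pre-post correlation .5), and give the power of the Holm rule by number of affected scores.

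**Cost.** If the outcome data have not been analysed, this is a change of SAP wording. The past tense suggests that they have been. In that case Holm can be applied to the existing p-values without new data, but the report must disclose that the rule, and the family if there is no prior record, were set afterwards. That limits false claims but cannot supply pre-specification. The statistical price is a stricter threshold per score, felt most when only one score is truly affected.

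### The planned 2×2 mixed ANOVA interaction is valid but ignores the baseline score; at the planned effect this costs about 5 points of power if the pre-post correlation is .5, half a point at .7 and nothing at .9

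*Combined protocol and SAP*

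**What the plan says.** The Statistical Analysis section gives one model for the cognitive variables: "mixed ANOVAs with 2 groups (active vs. sham; between-subjects) X 2 sessions (before vs. after intervention; within-subjects) were conducted". The decision rule is the interaction: "The effectiveness of the tDCS should be reflected by finding a significant interaction between the two independent variables". Simple-effects tests follow a significant interaction. No covariate is named there or elsewhere in the document.

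The sample size was set for the same test ("A priori power calculation for ANOVA repeated-measures within-between interaction") and "required a total sample of 32 participants to detect an effect size of .30 with 90% power", with alpha .05. The assumed pre-post correlation is not given.

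Under Randomisation, allocation is 1:1, "with gender as the stratum". Gender does not appear in the analysis model.

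**The concern.** With one measurement before and one after, the group-by-session interaction is algebraically a two-sample t-test on the change score. That test fixes the coefficient of the baseline score at 1. An ANCOVA on the post-intervention score estimates the coefficient instead. Under randomisation both target the same between-arm difference, but the change score carries more error variance unless r is very high.

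What is at stake is efficiency, not validity. The trial gives up some power, and any interval reported for the effect would be wider than it needs to be, although the baseline scores are already held. The excess variance comes from chance baseline imbalance, so imbalance is the source of this loss and not a second harm.

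Leaving out gender is a lesser point. Including the stratification factor would match the analysis to the design, but no power gain from it is shown here.

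**Working it through.** **Inputs from the Statistical Analysis and Randomisation sections.** N = 32, 1:1, so 16 per arm; f = .30 (read as Cohen's f under the G*Power default); power 90%; alpha .05; two groups; m = 2 sessions.

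**Assumptions.** r is not in the documents and is varied from .3 to .9. All 32 are analysed, scores are bivariate normal with equal SD at both sessions, and gender is split 8/8 in each arm and unrelated to outcome.

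**1. Reproduce the plan's figure.** For the within-between interaction, λ = f²·N·m/(1−r) with 1 and N−2 df. At r = .5, λ = 0.09 × 32 × 2 / 0.5 = 11.52, and power is 90.7%. The smallest even N that reaches 90% is 32, so the stated size reproduces at r = .5. Other correlations give 44 (r = .3), 20 (r = .7) and 10 (r = .9). Effect-size conventions without the factor m/(1−r) give about 120.

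**2. Put the effect on the score scale.** f = .30 with two groups and two sessions means interaction cell deviations of ±0.30 SD. The between-arm difference in change is therefore 4f = 4 × 0.30 = 1.2 single-session SD, whatever r is.

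**3. Compare error variances** (single-session variance = 1). Change score: 2(1−r). ANCOVA: 1−r². The difference is 2(1−r) − (1−r²) = (1−r)².

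- r = .5: 1.00 vs 0.75, excess 0.25
- r = .7: 0.60 vs 0.51, excess 0.09
- r = .9: 0.20 vs 0.19, excess 0.01

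**4. Precision and power.** Change-score power is from the noncentral t with 30 df and an SD of change of √(2(1−r)). ANCOVA power is from simulation, 200,000 trials per cell, with arm, baseline and gender in the model (28 df, two-sided .05). Half-widths of the 95% interval are simulation means in single-session SD and do not depend on the effect. Each entry is change score → ANCOVA.

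| r | CI half-width | Power, 1.2 SD (planned) | Power, 0.8 SD |
|---|---|---|---|
| .3 | 0.85 → 0.70 | 79.3% → 92.0% | not tabulated |
| .5 | 0.72 → 0.63 (12% narrower) | 90.7% → 96.0% | 59.1% → 69.8% |
| .6 | not tabulated | 95.6% → 98.0% | 68.7% → 76.4% |
| .7 | 0.55 → 0.52 (6%) | 98.9% → 99.4% | 80.7% → 85.1% |
| .8 | 0.45 → 0.44 (3%) | no gain | 93.3% → 94.6% |
| .9 | 0.32 → 0.32 (under 1%) | no gain | no gain |

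The 0.8 SD column is an illustration of a true effect smaller than planned; the plan does not state it.

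**5. Validity.** Simulated type I error at r = .5 and .7 is 5.0% for both tests. Some scales are capped (MMSE at 30, M@T at 50). With both scores capped 1 SD above the baseline mean, ANCOVA type I error is 4.9% and its advantage does not shrink at r = .5 or .7.

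**6. Which r is plausible.** Eligibility runs from healthy adults ("they must have a Montreal Cognitive Assessment (MCA) score greater than 26 points") to mild Alzheimer's disease ("with a MCA score ranging from 18 to 23 points and a GDS score between 3 and 4"). If the three groups are pooled, differences between them raise r. For example, with equal thirds at means −1, 0 and +1 within-group SD, the between-group variance is 2/3. A within-group r of .5 then gives a pooled r of (2/3 + 0.5)/(2/3 + 1) = .70.

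**The case against.** The strongest reply is that nothing here is an error. The interaction is valid, it is the test that was sized, and at r = .5 it meets its target (90.7% against 90%), so the 5 points are surplus. In the pooled example the gain at the planned effect is half a point. The larger gains need a low r or an effect smaller than the plan assumes, and the documents do not say which row applies. All of this stands, and it keeps the point at low priority.

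It is also fair that the fall from 5 points to none is partly a ceiling effect, because with f fixed the planned test is already near 99% at r = .7. If the effect shrank so that the ANOVA stayed at 90.7%, an approximate calculation gives losses of 5.9, 3.8 and 1.3 points at r = .5, .7 and .9. The half-widths avoid this problem and are the steadier measure; they show a modest gain.

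The plan specifies p-values and no confidence intervals, so the precision loss applies to any interval that is reported. The plan already rests efficacy on the between-arm interaction, so nothing here is a criticism of that choice. Finally, the section is in the past tense ("Data were analysed using SPSS 28"), so little may remain to change.

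None of this answers the central observation: the baseline is available, is not used as a covariate, and using it did no worse at any r examined.

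**Conclusion.** The concern holds as a point of efficiency, worth considering but not required for validity. At the correlation that reproduces the plan's own sample size (r = .5), leaving out the baseline costs about 5 points of power at the planned effect, and adjustment would narrow the interval by 12%. At r = .7 the figures are half a point and 6%; at r = .9 the loss is negligible. If the true difference were 0.8 SD, the loss would be about 11 points at r = .5 and 4 points at r = .7.

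These figures rest on an assumed r, on 16 analysed per arm and on equal SDs at the two sessions. They apply to one outcome at a time. The plan has several primary domains, and r may differ between tests, so a high r on one does not remove the loss on another.

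**What to change.** Analyse each post-intervention score by ANCOVA with arm, the same test's baseline score and gender in the model. Report the adjusted between-arm difference with its 95% confidence interval as the efficacy contrast, and give within-arm changes descriptively.

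Make this the primary analysis only if outcomes have not been seen. If they have, keep the planned ANOVA as primary and report the ANCOVA beside it as a labelled sensitivity analysis.

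The cost is two error degrees of freedom (30 to 28), a revised model sentence and one line in the sample-size statement giving the assumed pre-post correlation. No new data or software are needed.
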